- Treatment Period 2 consisting of 8 weeks where the participants will receive a treatment of once daily oral dose of dapagliflozin 10 mg in addition to the assigned dose of study drug. Only participants still taking their assigned treatment from Treatment Period 1 will progress to Treatment Period 2. Any participant with urine albumin to creatinine ratio (ACR) < 30 mg/g at Week 12 will be excluded from Treatment Period 2. The eligibility check to enter Treatment Period 2 will be done at Visit 7 (Week 12) using the last available urine ACR result, calculated as the geometric mean of the replicated measurements using 3 sequential first morning urine voids.
- Follow-up Period of up to 4 weeks.

The study will include a total of 10 visits which includes 2 visits during the Screening Period, 5 visits during the Treatment Period 1, 2 visits during the Treatment Period 2, and 1 visit during the Follow-up Period.

The expected total study duration, including the Screening Period, for each participant will be at least 28 weeks.

Data Monitoring Committee: Not applicable

Statistical Methods

The primary efficacy variable is the change from baseline in urine ACR at 20 weeks compared to placebo. Primary analyses will be based on the per protocol population where participants are evaluated according to the randomised treatment assignment. Urine ACR will be log-transformed and analysed using mixed model repeated measures method. The analysis model will include the fixed categorical effects of stratification factor, treatment, visit, and treatment-by-visit interaction, plus the continuous covariates of baseline log (urine ACR) and baseline log (urine ACR)-by-visit interaction. An unstructured covariance structure will be used for the within-participant errors. A homogeneity assessment between the DM and the non-DM sub-populations will be performed.

The change from baseline in urine ACR at 12 and 20 weeks will be analysed using the Multiple Comparison Procedure Modelling approach. Multiple candidate dose response models will be assessed. The best fitting model based on Akaike's Information Criteria will be used as a reference for dose selection.

Efficacy on current standard of care will be based on the Full Analysis population up to Week 12. The change in urine ACR from baseline to Week 12 will be log-transformed and be analysed similarly as the primary variable.

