- ^f All vital signs (blood pressure, heart rate, respiratory rate, body temperature, and pulse oximetry) will be measured with the participant is in a supine position having rested for at least 10 minutes before each reading and should be taken before any bloods draws. Vital signs should be collected pre-dose on the days of study drug dosing.
- ^g Optional, to be conducted only at study centres who agree to participate and have the appropriate facility to conduct the assessment. There is no requirement for all participants at centres undertaking the sub study to participate.
- ^h To be collected prior to study drug administration.
- ⁱ At specific PK sampling sites, for a sub-group of at least 80 participants (20 per dose group including placebo), 4 additional PK samples will be collected at Visit 5 within 1-2 h, 2-5 h, 5-8 h, and 8-12 h post-dose. Pre-dose samples will be collected for all participants. Each PK sample must be separated by at least 1 h.
- ^j Only if consent is obtained. The blood sample for Genomics Initiative will be obtained from the participants at Visit 3 prior to study drug administration (at or after randomisation). If for any reason the sample is not drawn at Visit 3, it may be taken at any visit until the last study visit. Only 1 sample should be collected per participant.
- ^k Participants will be requested to download an e-Diary application on their smartphones starting from Visit 3, in order to set study reminders and capture drug accountability throughout the treatment period, at sites where applicable. If needed, participants may be provided with a smartphone in order to use the application. Participants will be trained on how to use the application/device and the site will help the participants to login into the application for the first time. Data will be available to the site/Sponsor in real time. The participants who received a smartphone to use the e-Diary will return the smartphones at the last visit. Prior to deleting the e-Diary application from their personal smartphone, or returning a site provided smartphone, the participants will be requested to complete a satisfaction survey through the application (this survey is only applicable for e-Diary). Where completion of an e-Diary is not applicable, participant will be requested to complete a paper dosing diary.

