- ^l Phone call will occur after results from Screening Visit 1 are available and the participant is confirmed eligible in order to remind the participants to collect the first morning void urine samples and schedule the Screening Visit 2. If scheduled Visit 3 (Week 1) or Visit 7 (Week 12) will need to be delayed due to the need to repeat ABPM recording there is no need to repeat collection of the 3 urine samples.
- ^m Participants to collect first morning void urine samples on 3 consecutive days (ideally day of visit and each of the preceding 2 days [refrigerated overnight] which are returned on the day of visit). This collection may be repeated once during the course of screening.
- ⁿ Participants will be provided an ABPM cuff at Screening Visit 2 and Visit 6 (Week 8) and instructed to perform ABPM 24-hours before their next visit ie, Visit 3 (Week 1) and Visit 7 (Week 12), respectively. Site will be asked to call the participant the day prior to next visit as a reminder to complete assessments. The participant may also visit the site for APBM cuff placement 1 day before their next visit of scheduled assessment (ie, Visit 3 [Week 1] and Visit 7 [Week 12] respectively).
- ^o Sites should ensure that the validity criterion described in Section 8.2.5 is met prior to completing any other assessments at the visit. If the validity criterion is not met, the associated study visit may be rescheduled to allow for a repeat ABPM recording only if the rescheduled visit can be completed within the specified tolerance period for study visits:
- Visit 3: up to 72 hours following the originally scheduled visit for Visit 3 but no more than 32 days from Screening Visit 1
 - Visit 7: \pm 72 hours from Day 85
- If a repeat ABPM session is not possible, the study visit should proceed as indicated. In addition, the visit should also continue if the ABPM session does not meet the validity criterion after the repeat session.

^p Study drug refers to AZD5718/placebo during Treatment Period 1 and AZD5718/placebo + dapagliflozin during Treatment Period 2.

^q Site should follow-up directly with the participant via phone to remind the participant.

^r Participants to return all study drug dispensed at previous visits and only use the newly dispensed study drug. Participants should be reminded not to take study drug on the days of a study visit until instructed by the study site.

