6.4 Study Intervention Compliance

AZD5718 and placebo will be provided in blisters packed in child-resistant wallets. Enough tablets will be dispensed for daily dosing at home until the participant returns for the next study visit. Dapagliflozin will be provided in 75 cc high-density polyethylene bottle.

When the participants are dosed at the study centre, they will receive the study drugs directly from the Investigator or designee, under medical supervision. The date, and time if applicable, of dose administered in the clinic will be recorded in the source documents and recorded in

the electronic Case Report Form (eCRF). The dose of the study drugs and study participant identification will be confirmed at the time of dosing by a member of the study centre staff other than the person administering the study drug.

When the participants self-administer study drugs at home, compliance with study drugs will be assessed at each visit. Compliance will be assessed by direct questioning, counting returned tablets etc., during the study centre visits and documented in the source documents and eCRF. Deviation(s) from the prescribed dosage regimen should be recorded in the eCRF.

A record of the number of AZD5718/placebo and dapagliflozin tablets dispensed to and taken by each participant must be maintained and reconciled with study drugs and compliance records. Study drugs start and stop dates, including dates for intervention delays and/or dose reductions will also be recorded in the eCRF.

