7.3 Lost to Follow-up

A participant will be considered lost to follow-up if he or she repeatedly fails to return for scheduled visits and is unable to be contacted by the study centre.

The following actions must be taken if a participant fails to return to the study centre for a required study visit:

- The study centre must attempt to contact the participant and reschedule the missed visit as soon as possible and counsel the participant on the importance of maintaining the assigned visit schedule and ascertain whether or not the participant wishes to and/or should continue in the study.
- Before a participant is deemed lost to follow-up, the Investigator or designee must make every effort to regain contact with the participant (where possible, 3 telephone calls and, if necessary, a certified letter to the participant's last known mailing address or local equivalent methods). These contact attempts should be documented in the participant's medical record.
- Should the participant continue to be unreachable, he/she will be considered to have withdrawn from the study.
- Study centre personnel, or an independent third party, will attempt to collect the vital status of the participant within legal and ethical boundaries for all participants randomised, including those who did not get investigational product. Public sources may be searched for vital status information. If vital status is determined as deceased, this will be documented, and the participant will not be considered lost to follow-up. Sponsor personnel will not be involved in any attempts to collect vital status information.

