Measures to mitigate the additional risks caused by COVID-19 are:

- This study is going to start enrolling only when the Sponsor and CRO in collaboration deem it is safe to start the study. In addition, the study will not start until the local confinement measures or other safety restrictions linked to the COVID-19 pandemic imposed by the local authorities are compatible with safe conduct of the study.

- Current national laws and local recommendations for prevention of pandemic will be strictly adhered to.
- Participants will be closely monitored for any signs and symptoms of COVID-19, including fever, dry cough, dyspnoea, sore throat and fatigue throughout the study during the pandemic. Once clinical signs of infection are reported by participants, the Investigator needs to determine whether samples can be collected, and safety data can be recorded on site. If not, AEs and concomitant medications will be obtained via phone calls. The decision to continue with dosing the participant with the study drugs in the event of him/her showing symptoms of COVID-19 infection will be per Investigator's discretion.
- The probability of virus transmission will be controlled as much as possible by:
 - Advice for participant to adhere to local requirements for reduction of the public exposure while ambulatory.
 - Confirmation of COVID-19 infection by optional laboratory assessment will be conducted based on availability (test capacity and turnaround time) of approved tests and on Investigator's discretion.
 - Requesting all participants are contacted by phone 1 day prior to every visit for assessing COVID-19 symptoms and signs and are asked not to attend the site in case of suspected reports. In addition, participants are asked for any contact with a person who has tested positive for SARS-CoV-2. If applicable, participants will be referred to the local health care system for further follow-up and treatment.
 - Physical distancing and person-to-person contact restrictions will be applied during site visits and in-house confinement.
 - Where physical distancing is not possible, PPE will be used by study participants (surgical face mask, gloves) and staff (for example but not limited to masks, gloves, protectors, medical suits) if deemed appropriate by the Investigators and site staff and guided by local requirements.
 - Logistical improvements of the site and structural measures of the study site building will be implemented to further improve physical distancing.

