All visit-based summaries will use analysis visits. All post-randomisation scheduled and unscheduled visits (excluding Discontinuation Visit), will be mapped to an appropriate analysis visit as shown in [Table 2](#).

Table 2 Analysis Visit Windows

eCRF Visit	Target Day	Protocol Visit Window	Actual assessment day	Analysis visit
Visit 3 (randomisation)	D1	D1	D1	Randomisation
Visit 4 (Wk 2)	D15	D12 to D18	D2 to D21	Week 2
Visit 5 (Wk 4)	D29	D26 to D32	D22 to D42	Week 4
Visit 6 (Wk 8)	D57	D54 to D60	D43 to D71	Week 8
Visit 7 (Wk 12)	D85	D82 to D88	D72 to D88	Week 12
Visit 8 (Wk 16)	D113	D110 to D116	D89 to D127	Week 16
Visit 9 (Wk 20)	D141	D138 to D144	D128 to D144	Week 20
Visit 10 (Wk 24)	D169	D164 to D174	D145 to D183	Follow-up

Abbreviations: D = day; eCRF = electronic Case Report Form; Wk = week.

For visit-based summaries, if there is more than one value per participant within a time window, then the closest value will be summarised, or the earliest in the event the values are equidistant from the nominal visit date. The listings will highlight the value for that participant that went into the summary table, wherever feasible.

The Coronavirus Disease of 2019 (COVID-19) pandemic was declared by the World Health Organisation on 11 March 2020. Due to this, some COVID-19 specific summaries will be presented to summarise the impact of the pandemic.

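### SAP Table 2 assigns analysis visits by study day alone, so a pre-dapagliflozin Visit 7 after D88 or an on-treatment Visit 9 after D144 loses its slot: a minor point, cheap to fix

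*SAP*

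**What the plan says.** SAP section 4.2 counts study day from randomisation and says: "All post-randomisation scheduled and unscheduled visits (excluding Discontinuation Visit), will be mapped to an appropriate analysis visit". Table 2 gives the day ranges. Week 12 (target D85) runs from D72 to D88, Week 16 (D113) from D89 to D127, Week 20 (D141) from D128 to D144, and Follow-up (D169) from D145 to D183. If several values fall in one window, "then the closest value will be summarised, or the earliest in the event the values are equidistant from the nominal visit date". Nothing in the table depends on the eCRF visit, the first dapagliflozin dose or the last dose of study drug.

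The protocol Synopsis places the switch in treatment at Visit 7: "The eligibility check to enter Treatment Period 2 will be done at Visit 7 (Week 12) using the last available urine ACR result". A footnote to the Schedule of Activities says of the urine ACR samples: "To be collected prior to study drug administration".

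The primary model (SAP 4.9.2.1) is an MMRM over Weeks 2, 4, 8, 12, 16 and 20, with the contrast at Week 20. Missing urine ACR is not imputed (SAP 4.9.1.4). Week 12 eGFR is analysed by a by-visit ANCOVA (SAP 4.9.3.2).

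**The concern.** A scheduled Visit 7 urine sample precedes dapagliflozin whatever its date, because entry to Treatment Period 2 is decided at that visit and the sample is taken before dosing. A Visit 9 sample from a participant still taking both drugs is likewise a valid end-of-treatment value a few days after D144. Table 2 removes both from their slots once the date passes the limit.

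Late visits are foreseeable. Protocol section 7.3 says of missed visits: "The study centre must attempt to contact the participant and reschedule the missed visit as soon as possible". Protocol Appendix F says that participants called before a visit to check for COVID-19 "are asked not to attend the site in case of suspected reports". A repeat ABPM recording is not a cause, because that delay of Visit 7 is held to within "72 hours from Day 85".

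At stake is a completer who contributes no primary Week 20 value although one was collected. For Week 12 eGFR, the by-visit ANCOVA borrows nothing from other visits, so the participant drops out of that comparison.

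**Working it through.** **Inputs.** Target days and windows are from SAP Table 2. The ±3-day tolerance for Visits 7 and 9 and the Visit 8 tolerance are from the Schedule of Activities. The 35 tablets per dapagliflozin bottle are from protocol Table 3. The 340 participants completing treatment are from SAP 4.14.

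**Step 1: reproduce the limits.** 85 + 3 = D88 and 141 + 3 = D144, which are the protocol limits exactly.

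**Step 2: compare each boundary with the midpoint of adjacent targets.**

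| Boundary | Table 2 | Midpoint |
|---|---|---|
| Week 2 / 4 | D21/22 | (15+29)/2 = D22 |
| Week 4 / 8 | D42/43 | (29+57)/2 = D43 |
| Week 8 / 12 | D71/72 | (57+85)/2 = D71 |
| Week 12 / 16 | D88/89 | (85+113)/2 = D99 |
| Week 16 / 20 | D127/128 | (113+141)/2 = D127 |
| Week 20 / Follow-up | D144/145 | (141+169)/2 = D155 |

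Four boundaries are within 1 day of the midpoint. The other two are 11 days before it (99 − 88 = 11; 155 − 144 = 11). Weeks 12 and 20 therefore accept values 13 days early (85 − 72; 141 − 128) but only 3 days late.

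**Step 3: map a late visit.**
- Visit 7 on D89 maps to Week 16. With Visit 8 on D113, the distances from target are 24 and 0 days, so Visit 8 is used and the Visit 7 value is used nowhere. With Visit 8 missing, the pre-dapagliflozin value stands as Week 16. Week 12 is empty either way, unless another value lies in D72 to D88.
- Visit 9 on D145 maps to Follow-up and Week 20 is empty, unless another value lies in D128 to D144. With Visit 10 on D169, the late Visit 9 value is used nowhere.

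**Step 4: the proxy can fail the other way.** With Visit 7 on D82 and an unscheduled sample after dapagliflozin on D86, both map to Week 12. The distances are 3 days and 1 day, so the post-dapagliflozin value is chosen.

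**Step 5: how late can Visit 9 be and still be on dapagliflozin?** Assume one bottle per dispensing visit, with the first tablet on the day of Visit 8. The last tablet day is Visit 8 + 34: D144, D147 or D150 for Visit 8 on D110, D113 or D116. Visit 9 dates after D144 that follow a dose the day before are then D145 only (1 day), D145–D148 (4 days) or D145–D151 (7 days).

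**Step 6: size.** The number of late visits is not given, so the late share f is assumed. Let R² be the share of Week 20 variance explained by earlier visits. The standard error ratio is √(R² + (1 − R²)/(1 − f)).

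| f | 340 × f | SE rise, R² = 0 | SE rise, R² = 0.5 |
|---|---|---|---|
| 1% | 3.4 | 0.5% | 0.3% |
| 2% | 6.8 | 1.0% | 0.5% |
| 5% | 17 | 2.6% | 1.3% |
| 10% | 34 | 5.4% | 2.7% |

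Example: f = 10% and R² = 0 gives √(1/0.90) = 1.054.

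**The case against.** **The limits look deliberate.** The two short boundaries fall where dapagliflozin starts and where treatment ends, and they equal the protocol tolerance. They do exclude most contaminated values. This stands, and it is why widening the windows to the midpoint would not be enough. It does not make day a good substitute for dosing dates, which are recorded.

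**Table 2 is stated for visit-based summaries.** The SAP does not say that it defines visits in the MMRM or the eGFR ANCOVA, and SAP 4.10.5 uses a different rule for its own by-visit safety summaries. This stands as a caveat. No other visit definition is given for those two models, so Table 2 is the natural reading.

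**Some affected participants may not be in the primary set.** COVID-19-related missed visits or assessments with a significant effect on the data are an important deviation (SAP 4.4.2). The deviations that lead to exclusion are listed in a separate specification. This also stands.

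Three stronger inferences are tempting but not supported:
- *That a late Week 12 ABPM recording is excluded.* SAP 4.9.3.3 has its own session rules: it chooses between scheduled and repeat sessions by the percentage of successful readings, not by closeness to the target day. Exclusion through Table 2 is not established.
- *That 11 days of valid Week 20 values are lost.* Protocol section 6.4 says: "Enough tablets will be dispensed for daily dosing at home until the participant returns for the next study visit". But the bottle size supports only about 1 to 7 days of dapagliflozin cover after D144 (Step 5). For Visit 7, cover with AZD5718 or placebo is unknown, because tablets per wallet are not stated.
- *That 4 days late is an exact threshold for urine ACR.* Each value combines voids from three consecutive days, ideally the visit day and the two before, and the SAP does not name the assessment date. If it is the visit day, the Week 12 slot is lost from a visit on D89. If it is the middle or first void, it is lost from D90 or D91.

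**Conclusion.** The point holds as a minor one: a cheap improvement to the SAP. By the rule as written, a pre-dapagliflozin Visit 7 dated D89 or later leaves Week 12, and an on-treatment Visit 9 dated D145 or later leaves Week 20 and takes the primary value with it. Only visits outside the protocol window are affected.

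The likely effect is a small loss of precision: the standard error rises by about 0.3% to 5% if 1% to 10% of Week 20 values are late. There should be little bias. The conclusion rests on three assumptions: that Table 2 governs the MMRM and the eGFR ANCOVA, that the late shares are of this order, and that the late participant was still on treatment. A reader might infer that the primary analysis is materially distorted. The documents give no late-visit count, and nothing in them supports that.

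**What to change.** Amend SAP 4.2 before database lock so that samples are classified by dosing dates before the day windows are applied:

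- (a) A scheduled Visit 7 value taken before the first dapagliflozin dose, and while on AZD5718 or placebo, counts as Week 12 up to a stated day limit (for example D99). No pre-dapagliflozin value may fill Week 16 or Week 20.
- (b) A Visit 9 value after D144 counts as Week 20 only if taken within a stated number of days of the last dose of both study drugs, and up to a stated day limit.
- (c) Post-dapagliflozin values may not enter Week 12, and off-treatment values after D144 may not enter Week 20. This keeps the present protection and closes the gap in Step 4.
- (d) State that these windows define the visits in the MMRM and eGFR models, and which date is the assessment day for the three-day urine ACR collection.

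The cost is SAP wording and a little derivation programming, with no new data. The downside is that a few Week 12 and Week 20 values will reflect slightly longer exposure.

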4.3 Software

All report outputs will be produced using SAS® version 9.4 or a later version in a secure and validated environment.

4.4 Study Participants

4.4.1 Disposition of Participants

A clear accounting of the disposition of all participants who enter the study will be provided, from screening to study completion.

The following summaries will be provided:

- A summary of the number of participants screened, screen failures, enrolled into the study, randomised, treated, completing Treatment Period 1, completing Treatment Period 2 and completing the study, by treatment group and overall. In addition, reasons for not being treated, not completing Treatment Period 1, not completing Treatment Period 2 and not completing the study will be summarised by treatment group and overall (Analysis set: All participants).
- A summary of the number of participants randomised per region, country and centre, by treatment group and overall (Analysis Population: Randomised participants).
- A summary of Interactive Voice Recognition System (IVRS) stratification factors ie, DKD status (DKD participants, non-DKD participants), SGLT2i history (with SGLT2i background, without SGLT2i background) and region (Japan, Rest of World) at randomisation by treatment group and overall (Analysis Population: Randomised participants).

By-participant listings of disposition details for discontinued participants and participants completing the study will be provided. In addition, a by-participant listing of the randomisation scheme and codes will be provided.

